4.1.2. Duration of Patient Participation

Patients will initially be involved (from screening to follow-up) in the study for approximately 52–56 weeks. This period includes a screening and baseline period that will last up to 28 days, a 48-week Treatment Phase and a potentially a 30-day safety follow up.

Patients who complete the 48-week open label Treatment Phase may choose to consent to roll into an Extension Phase which will last until either SMT C1100 is approved in the relevant countries or development of SMT C1100 is discontinued. Patients who are enrolled in the Extension Phase may have home visits if only vital signs and blood samples are being collected at a scheduled visit (Weeks 12 and 36 of each year of the Extension Phase); if this occurs then AE and concomitant medication checks will be performed in a documented telephone call. The patient's IMP supply should be considered when determining whether a home and telephone visit are appropriate. Patients in the Extension Phase will have a 30-day safety follow up if/when the study is stopped.

Study Number: SMT C11005	Compound No.: SMT C1100
Protocol	Version: 5.0 24Feb2017

Additionally, the DMC and/or the Sponsor may recommend amending the duration of the study based on safety or efficacy findings.

4.2. Stopping Rules

4.2.1. Study Stopping Rules

Routine independent DMC meetings will be held during the course of the study in accordance with ICH-GCP and the DMC charter. Additional meetings can be requested at the DMC's discretion at any point in the study.

The responsibilities of the DMC include: (1) ongoing assessment of safety data during the trial for the purposes of safeguarding the interests of trial participants, (2) assessment of pharmacokinetic data and its relationship to the AE profile, (3) oversight of clinical trial conduct including general safety and International Council on Harmonization (ICH) GCP procedures. To enhance the integrity of the trial, the DMC may formulate recommendations relating to the selection/recruitment/retention of patients, improving adherence to protocol-specified treatment and retention of patients and procedures for data management and quality control. Based on its review of the data during periodic meetings, the DMC may provide recommendations about stopping, modifying, or continuing the trial. Summit will retain ultimate responsibility on decision making.

Summit reserves the right, at any time, to prematurely terminate the trial or trial sites. Premature termination of the trial could be for scientific or administrative reasons or for any other valid and/or ethical reason or if any safety issues arises and the overall risk/benefit evaluation changes and is no longer in favour of continuation.

4.2.2. Individual Stopping Rules

The pharmacokinetics of SMT C1100 parent and metabolites, and their relationship with all safety parameters, will be reviewed on an ongoing basis by the Sponsor and the DMC. As this is an open-label study, the decision to stop individual patients may be made on a case-by-case basis. The DMC can also recommend, in individual patients, a lowering of the SMT C1100 dose.

If a patient's results meet either of the criteria below, dosing should be stopped and the tests should be repeated as soon as possible. If the repeated results still meet this criterion, the study drug will be permanently stopped and may not be restarted although the patient will continue to be followed for functional and MRI assessments for the duration of the study. If the patient is withdrawn from the study, a follow up visit should be arranged:

- GLDH \geq 3x ULN

Study Number: SMT C11005 Protocol	Compound No.: SMT C1100 Version: 5.0 24Feb2017
---	---

OR

- Bilirubin $\geq 2x$ ULN together with an INR $\geq 1.5x$ ULN (Cohort 2 and 3 only)

Any intolerable AE or SAE that is at least possibly related to study drug should lead to a temporary discontinuation of the patient's study treatment. After resolution of the intolerable AE or SAE, the Investigator, in discussion with the Sponsor, may decide to either permanently discontinue the patient's study treatment, or, if recommended by the DMC and Sponsor reinstate treatment but reduce their *bid* dose to 1.25 g for Cohort 1 and 3 or reduce the frequency to once-daily dosing (2.5 g or 1.25 g for Cohorts 1 and 3; 1 g for Cohort 2; see Section 8.1.1). If a lowered dose is tolerated for at least 2 weeks the Investigator can, based on the recommendation of the DMC and Sponsor escalate the dose up to the original strength. Once-daily dosing should occur in the morning.

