Haematology, coagulation, clinical chemistry & urinalysis	X	X	X		X	X	X	X	X	X
Liver function tests, including glutamate dehydrogenase; amylase and lipase	X		X	X	X	X	X	X	X	X
C4 and FGF19	X					X ⁱ		X ^f		X
NSAA	X					X		X	X	X
10 metre run/walk	X					X		X	X	X
Six minute walk distance/test	X					X		X	X	X
PODCI	X					X		X	X	X
PUL ^b	X					X		X	X	X
Blood biomarker separate sample ^c	X	X		X		X		X	X	X

Study Number: SMT C11005

Protocol

Compound No.: SMT C1100

Version: 5.0 24Feb2017

	Screening Phase	Treatment Phase Cohort 3							Early termination visit	End of study visit
		D-28 to D-1	W1/Day 1	W1/Day 7 ^h	W4 +/- 1 w	W12 +/- 2 w	W24 +/- 2 w	W36 +/- 2 w		
SMTC1100 parent & metabolites sparse pharmacokinetic sampling ^e		X	X ^h	X	X	X	X	X	X	X
SMT C1100 bid dosing		X	X	X	X	X	X	X		
Adverse event recording	X	X	X	X	X	X	X	X	X	X
Prior and concomitant medications	X	X	X	X	X	X	X	X	X	X

If multiple assessments are at the same time point, it is appreciated that some deviation in timing will be necessary. A ± 15 minute window is acceptable with pharmacokinetic samples being performed as close to scheduled time point as possible. Please see the study manual for more information on timing.

- a. Pulmonary assessments include forced expiratory volume in 1 second, peak expiratory flow, forced vital capacity, maximum inspiratory pressure, maximum expiratory pressure, peak cough flow and sniff nasal inspiratory pressure.
- b. Where a biopsy is performed at the same visit this procedure should be performed prior to the biopsy.
- c. Plasma biomarkers include creatine kinase, matrix metalloproteinase 9, and others, as well as quantification of changes of proteins. Note: creatinine kinase and MMP-9 will not be collected at Week 1.
- d. ECGs to be performed pre-AM dose and 0.5, 2, 4 and 6 h post-AM dose
- e. Each patient will have three PK samples taken at pre-AM dose and, 3 and 6 h post-AM dose
- f. Samples to be collected pre-AM dose, 3 h post- AM dose, pre-PM dose and 4 h post-PM dose; At Week 1, only AM samples apply
- g. If not performed in the last 6 weeks.
- h. One PK sample collected at 4 h post-am dose.
- i. Laboratory assessments may be conducted by the sponsor-provided home nursing vendor on Day 7 and Week 4.

Study Number: SMT C11005
Protocol

Compound No.: SMT C1100
Version: 5.0 24Feb2017

Time and Events Table

Extension phase

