Abnormal liver function tests were seen in patients with DMD dosed with the F6 formulation in the SMT C11004 study. AST and ALT are enzymes already raised in patients with DMD (although the likely source is muscle) and, as such, further elevations in these enzymes due to liver toxicity may be difficult to see. GLDH is being evaluated and is considered a more specific liver enzyme marker [Schomaker *et al*, 2013]. In addition, liver disease is characterised by reduced synthesis of the procoagulant proteins II, VII, IX, X, as well as factor V and factor XI. These factor deficiencies directly affect the standard coagulation measures available in clinical laboratories, mainly the prothrombin time (PT) and its standardisation, the international normalised ratio (INR), and to a lesser extent, the activated partial thromboplastin time (aPTT) [Northup and Caldwell, 2013]. Therefore, as a precaution and as a means to monitor liver dysfunction both GLDH and coagulation times will be measured.

Finally, during the SMT C11004 study stopping criteria based on liver function were developed. These are outlined below and will be followed during this study, as applicable.

If a patient's results meet either of the criteria below, dosing should be stopped and the tests should be repeated as soon as possible. If the repeated results still meet this criterion, the study drug will be permanently stopped and may not be restarted although the patient will continue to be followed for functional and MRI assessments for the duration of the study. If the patient is withdrawn from the study, a follow up visit should be arranged:

GLDH \geq 3x upper limit of normal (ULN)

OR

Bilirubin \geq 2x ULN together with an INR \geq 1.5x ULN (Cohort 2 and 3 only)

Patients in this study will receive either SMT C1100 2.5 g *bid* F3 formulation (Cohort 1 and Cohort 3) or SMT C1100 1 g *bid* F6 formulation (Cohort 2) for 48 weeks. Previous exposure at the F3 formulation 2.5 g *bid* dose level in the paediatric DMD population has

Study Number: SMT C11005	Compound No.: SMT C1100
Protocol	Version: 5.0 24Feb2017

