been limited to 14 days whilst that for F6 formulation 1 g *bid* dose level has been limited to 7 days. Neither has been associated with any safety signals except the observation of pale stools with both formulations and transient elevations in LFTs for the F6 formulation. The pharmacokinetics of SMT C1100 parent and metabolites, and the safety data, will be reviewed on an ongoing basis by the Sponsor and the data monitoring committee (DMC). As this is an open-label study, the Investigator should determine if an SAE is related to IMP and consider modifying the dose given. Serious AEs considered at least possibly related to IMP may require a dose reduction, a temporary hold or permanent discontinuation, with prior consultation and agreement with the Sponsor.

A risk relating to the study design is the requirement for the paediatric patients enrolled in this study to undergo up to two muscle biopsies, which will include the use of anaesthesia. This procedure may cause some discomfort but will be done with the assent of the patient, consent of their parents (or other adult legally responsible for them) and in a sensitive way that takes into account their age. The procedure will be explained to the patients in advance in an age appropriate manner and they and their parents will be given an opportunity to ask any questions they have relating to the procedure. Appropriate pain-relief will be made available following each biopsy.

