To date, no major safety signal has been observed in either the animal toxicology studies or in the human clinical studies. Preclinical data suggests an interaction with the hERG channel, interactions with substrates of CYP2B6 and BCRP, and inhibition of the MAO-B enzyme. These risks are mitigated by the assessment of multiple ECGs taken at frequent time points throughout the study, the exclusion of substrates of CYP2B6 and BCRP and the exclusion of drugs that have serotonergic, norepinephrinergic or dopaminergic activity. One SAE was reported following dosing with the F6 formulation in Study SMT C11004 but no SAES reported in the ongoing PhaseOut DMD study (SMT C11005) with the majority of AEs reported being mild (data up to 07 Feb 2017).

Although abnormal LFTs have previously been seen in patients with DMD treated with the F6 formulation, these abnormal values quickly returned to baseline levels after dosing with the IMP was stopped. Additional safety tests including GLDH and measurement of coagulation parameters have been added to the protocol and robust stopping criteria defined. Subjects in the SMT C11005 study may continue to receive SMT C1100 following their Week 48 visit, and will provide long term safety data, useful long term efficacy data, and also provide an opportunity to compare any beneficial effects to natural history data.

The Sponsor therefore believes the current risk benefit ratio for the SMT C11005 study is favourable.

However, the Sponsor will immediately notify the Principal Investigators and Regulatory Agencies if any additional safety or toxicology information becomes available during the study. In addition, an independent DMC will, on a regular basis, review all pertinent pharmacokinetic and safety data and make recommendations on dosage adjustments, if needed during the main part of the study.

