6.4.6. Laboratory Assessments

Please note Day 7 (Cohort 2 and 3 only), Week 4 (all cohorts) and Week 8 (Cohort 1 and 2 only) assessments may be conducted by the sponsor-provided home nursing vendor.

Patients who are enrolled in the Extension Phase may have home visits if only vitals and blood samples are being collected at a scheduled visit; if this occurs then AE and concomitant medication checks will be performed in a documented telephone call.

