5.4.2 Laboratory Data

Laboratory parameters will be reported in International System of Units (SI).

Coagulation parameters will only be assessed in Cohorts 2 and 3.

The table below details the times when laboratory measurements will be taken:

| Visit | Cohort | | |
|------------------|---------------|---------------------|---------------------|
| | 1 | 2 | 3 |
| Screening | H, CC, U, LFT | H, CC, U, LFT, Coag | H, CC, U, LFT, Coag |
| Baseline Phase | H, CC, U, LFT | H, CC, U, LFT, Coag | |
| Day 1 | LFT | LFT | H, CC, U, Coag |
| Day 7 | | LFT, Coag | H, CC, U, LFT, Coag |
| Week 4 | LFT | LFT | LFT |
| Week 8 | LFT | LFT | |
| Week 12 | H, CC, U, LFT | H, CC, U, LF, Coag | H, CC, U, LFT, Coag |
| Week 24 | H, CC, U, LFT | H, CC, U, LF, Coag | H, CC, U, LFT, Coag |
| Week 36 | H, CC, U, LFT | H, CC, U, LFT, Coag | H, CC, U, LFT, Coag |
| Week 48 | H, CC, U, LFT | H, CC, U, LFT, Coag | H, CC, U, LFT, Coag |
| Extension Visits | H, CC, U, LFT | H, CC, U, LFT, Coag | H, CC, U, LFT, Coag |

H: Haematology, CC: Clinical Chemistry, U: Urinalysis, LFT: Liver Function Tests, Coag: Coagulation parameters

Changes from baseline will be calculated.

Some laboratory parameters will be categorized to assist identifying values of potential concern. Details are provided in [Section 9.8.3](#).

The following parameters will be assessed relative to the upper limit of normal, e.g. value/ULN:

- Alkaline Phosphatase
- ALT
- AST
- Creatine kinase
- GLDH
- Total Bilirubin

For those parameters recorded as $>x$ or $<x$ a small value (0.01) will be added or subtracted from the value x respectively prior to performing analyses. Listings will present the original value.

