9.8.3 Laboratory Data

Descriptive summaries of absolute values and changes from baseline will be provided for numerical laboratory parameters for each visit. At each visit the number of subjects with 'High', 'Low' or 'Normal' with respect to their reference range will be tabulated.

The categorical lab results will only be listed.

The number (%) of subjects who fulfill the following liver function test criteria at any time after the start of dosing will be tabulated:

- ALT \geq ULN, $\geq 2 \times$ ULN, $\geq 3 \times$ ULN
- AST \geq ULN, $\geq 2 \times$ ULN, $\geq 3 \times$ ULN
- Total Bilirubin \geq ULN, $\geq 2 \times$ ULN
- alkaline phosphatase $\geq 1.5 \times$ ULN
- GLDH \geq ULN

The number (%) of subjects who fulfill Hy's Law (ALT or AST $> 3 \times$ ULN + bilirubin $> 2 \times$ ULN, Alkaline Phosphatase must also be \leq ULN) will also be tabulated.

Separate summaries will be generated for the first 24 weeks, first 48 weeks and for the whole study.

These parameters will be listed, along with the value related to ULN (i.e. value/ULN) for subjects who fulfill one of the following criteria:

- ALT $\geq 2 \times$ ULN
- AST $\geq 2 \times$ ULN
- Total Bilirubin $\geq 2 \times$ ULN
- alkaline phosphatase $\geq 1.5 \times$ ULN
- GLDH \geq ULN

For each liver function test (ALT, AST, total bilirubin, alkaline phosphatase, GLDH) and creatine kinase, the value related to ULN (i.e. value/ULN) will be plotted against time in trellis plots, where each subject will have their own plot and the legend distinguishing the laboratory parameter. The plot will use a log10 scale with the axis labels reflecting the actual value (e.g. 1, 10, 100...).

For Cohort 2 the number (%) of subjects who fulfill the following coagulation test criteria at any time after the start of dosing will be tabulated:

- International Normalised Ratio $\geq 1.5 \times$ ULN
- Activate Partial Thromboplastin $>$ ULN

Separate summaries will be generated for the first 24 weeks, first 48 weeks and for the whole study.

A listing will also present all data that meet these criteria along with the value related to ULN (i.e. value/ULN).

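### Cohorts 2 and 3: bilirubin is drawn without INR at Week 4 (both cohorts) and Week 8 (Cohort 2), so the joint bilirubin-INR stopping rule cannot be evaluated on those scheduled samples

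*Protocol*

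**What the plan says.** Protocol 4.2.2, in the same terms as 1.3.4, gives two liver criteria for stopping an individual boy. The first is GLDH of at least 3x ULN. The second, for Cohorts 2 and 3 only, is bilirubin of at least twice the "ULN together with an INR" of at least 1.5 times ULN. If either is met, dosing stops and the tests are repeated. If the repeat confirms the result, the drug is stopped for good.

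Protocol 6.4.6.4 places INR in the coagulation panel, drawn at the times in the Time and Events tables. Protocol 6.4.6.2 names one additional coagulation draw, at Day 7.

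The SAP 5.4.2 schedule has the row "Week 4 | LFT | LFT | LFT" for the three cohorts, and its Week 8 row shows only liver function tests, for Cohorts 1 and 2. Coagulation appears beside liver tests at Day 7 and again from Week 12. In the Cohort 3 Time and Events table, the row "Haematology, coagulation, clinical chemistry & urinalysis" is blank at Week 4 while the liver function row is marked. SAP 9.8.3 shows what a liver function test covers: "For each liver function test (ALT, AST, total bilirubin, alkaline phosphatase, GLDH) and creatine kinase".

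Protocol 1.3.4 presents the coagulation tests as part of liver surveillance: "as a means to monitor liver dysfunction both GLDH and coagulation times will be measured". The risk-benefit statement in 1.3.5 relies on them: "Additional safety tests including GLDH and measurement of coagulation parameters have been added to the protocol and robust stopping criteria defined".

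**The concern.** A two-part rule works only if both parts are measured on the same occasion, or if an abnormal first part triggers the second. At these visits bilirubin is measured and INR is not. The instruction to repeat the tests does not help, because it begins only once a criterion has been met, and bilirubin alone cannot meet this one.

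The timing adds weight. According to 1.3.4, earlier exposure at F3 2.5 g bid had "been limited to 14 days whilst that for F6 formulation" at 1 g bid was limited to 7 days. Week 4 is therefore the first scheduled liver check beyond what had been studied at either dose.

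A boy with bilirubin at or above 2x ULN, INR at or above 1.5x ULN and GLDH below 3x ULN at Week 4 or 8 would satisfy a stopping rule that his scheduled samples could not reveal. Whether he stopped would depend on the investigator's discretion or on an adverse-event hold.

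GLDH does not fully cover this case. In the earlier F6 study the one serious adverse event was mainly raised conjugated bilirubin (Protocol 1.1), with a positive rechallenge (1.1.3). Total bilirubin exceeded ULN in three of eight boys, while only one had GLDH above 2x ULN (1.3.3), so at most one could have reached the 3x threshold. Section 8.2 names OATP1B1 inhibition by the metabolites as a possible contributor to the raised bilirubin. ALT and AST are of limited use because the disease itself raises them.

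**Working it through.** The plan states no figure on this point. The check compares the two inputs of the rule visit by visit and then counts.

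**Inputs**
- Planned numbers: about 10 boys in Cohort 2 and 15 in Cohort 3 (Protocol 5.1).
- Visits and panels: SAP 5.4.2, compared with the protocol's Time and Events tables.
- Bilirubin is counted as part of the liver function tests (SAP 9.8.3).
- Target days: Day 7, and Day 84 for Week 12 (SAP 5.1). The Week 12 visit window is ±2 weeks (Time and Events tables).

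**Scheduled visits after Day 1**

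| Visit | Cohort 2 bilirubin | Cohort 2 INR | Cohort 3 bilirubin | Cohort 3 INR |
|---|---|---|---|---|
| Day 7 | yes | yes | yes | yes |
| Week 4 | yes | **no** | yes | **no** |
| Week 8 | yes | **no** | no visit | no visit |
| Week 12 | yes | yes | yes | yes |
| Weeks 24, 36, 48 | yes | yes | yes | yes |

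The columns of the protocol's Cohorts 1 and 2 table do not line up cleanly in the text version, but Weeks 4 and 8 are blank for coagulation on either reading. The SAP table is intact and agrees.

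**Interval between scheduled INRs**
- Nominal: 84 − 7 = 77 days.
- With the Week 12 window: from 70 − 7 = 63 to 98 − 7 = 91 days.

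**Boy-visits at which the rule cannot be evaluated**
- Without INR: 10 × 2 + 15 × 1 = 35.
- Up to Week 12, all liver-test visits: 10 × 4 + 15 × 3 = 85. Share: 35/85 = 41%. By cohort: 20/40 = 50% in Cohort 2 and 15/45 = 33% in Cohort 3.
- Up to Week 48, all liver-test visits: 10 × 7 + 15 × 6 = 160. Share: 35/160 = 22%. By cohort: 20/70 = 29% and 15/90 = 17%.

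Early termination and end-of-study visits are not counted.

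**If the liver panel did not include bilirubin.** The protocol does not itemise the panel. On that reading both inputs would be missing at Weeks 4 and 8, and the rule would still not be evaluable.

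**The case against.** The strongest reply is that the rule fails only on scheduled samples. A bilirubin above 2x ULN would lead most investigators to order an INR, and nothing forbids it. The Sponsor and the DMC review safety data continuously, stopping can be decided case by case, and GLDH, which the protocol regards as the more reliable marker of liver cell necrosis, is still drawn. The study reference and laboratory manuals may also contain a reflex test.

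The schedule has a visible logic too. The serious event arose in a study with 7-day dosing periods, and Day 7 is where both panels are paired. Fifteen of the 25 boys take F3, whereas the protocol attributes the liver signal to F6. Cohort 1, on the same F3 dose, has no INR criterion at all. The 41% depends on stopping the count at Week 12, and no estimate exists of how often high bilirubin, high INR and GLDH below threshold would coincide.

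Much of this stands as context. The joint event may be rare, the percentages measure coverage and not risk, and the identified signal concerns the roughly 10 boys on F6. What does not stand is the idea that the text closes the gap. An optional INR leaves a protocol-defined stop to discretion, and a reflex test in an unseen manual is speculation. Prompting is also slow here: blood is analysed centrally and "Week 4 (all cohorts) and Week 8 (Cohort 1 and 2 only) assessments may be conducted by the sponsor-provided home nursing vendor", so an INR ordered after the bilirubin result needs a second draw.

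**Conclusion.** The concern holds. Following the stated schedule leaves one of the two liver stopping criteria without one of its inputs at Week 4 in Cohorts 2 and 3 and at Week 8 in Cohort 2. That is 35 boy-visits: 41% of post-dose liver-test boy-visits up to Week 12 and 22% up to Week 48, all at Weeks 4 and 8. It does not remove all protection, because the GLDH criterion, case-by-case stopping and the hold for related intolerable or serious events remain. It should be corrected because it affects a permanent-stop rule in children at the first checks beyond earlier exposure, and the remedy is small.

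The counts assume full enrolment at the planned numbers, no dropout and bilirubin within the liver panel. The conclusion is limited to scheduled samples and to what the protocol and SAP say.

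**What to change.** Add coagulation (INR) to the existing blood draw at Week 4 in Cohorts 2 and 3 and at Week 8 in Cohort 2, in both Time and Events tables and in SAP 5.4.2. Paired coverage after Day 1 up to Week 48 would rise from 5 of 7 visits to 7 of 7 in Cohort 2, and from 5 of 6 to 6 of 6 in Cohort 3.

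At minimum, add one sentence to Protocol 1.3.4 and 4.2.2: if bilirubin is at least 2x ULN and no INR is available from the same draw, obtain one promptly. This avoids extra tubes in boys with normal bilirubin, but costs a second draw and some delay in those affected.

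The thresholds stay as they are, and a boy with isolated raised bilirubin would not be stopped by either change. The cost is at most about 35 tubes (10 × 2 + 15 × 1), revised schedule wording and an updated home-nursing kit, with no new visits or staff. Either version changes the protocol text, so it needs an amendment with ethics review (Protocol 13.1). As the study is already running, it helps only boys who have not yet passed these visits.
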